2.1.3 Exploratory Efficacy Objective

The exploratory efficacy objective for this study is to evaluate the efficacy of GDC-9545 plus palbociclib compared with anastrozole plus palbociclib on the basis of the following endpoints:

- Central assessment of changes in Ki67 scores from baseline to surgery and from Week 2 to surgery
- CCCA rate as defined as proportion of patients with centrally assessed Ki67 scores $\leq 2.7\%$ stained nuclei upon treatment at surgery or post-treatment biopsy (see Section 4.5.10)
- Pathological complete response (pCR) rate (ypT0/is, ypN0) of GDC-9545 plus palbociclib compared with anastrozole plus palbociclib

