4.2 METHOD OF TREATMENT ASSIGNMENT

This is a randomized, open-label study. After initial written informed consent has been obtained, all screening procedures and assessments have been completed, and eligibility has been established for a patient, the study site will obtain the patient's identification number and treatment assignment from an interactive voice or web-based response system (IxRS).

Patients will be randomly assigned to one of two treatment arms: experimental arm or control arm. Randomization will occur in a 1:1 ratio through use of a permuted-block randomization method to ensure a balanced assignment to each treatment arm. Randomization will be stratified according to the following criteria:

- cT status: cT1c–cT2 versus cT3–cT4a–c
- Ki67 score: <20% versus ≥20%
- PgR status: positive versus negative

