6.1 DETERMINATION OF SAMPLE SIZE

The sample size is determined by the primary efficacy endpoint, central assessment Ki67 change from baseline to Week 2 (see details in Section 6.4.1). Approximately 202 patients will need to be randomized in a 1:1 ratio to either the experimental arm (GDC-9545) or control arm (anastrozole) to allow for 80% power to detect an 8% improvement for mean Ki67 change in 2 weeks from -75% in the control arm to -83% in the experimental arm at one-sided 10% level of significance. This target improvement also corresponds to an effect size of 0.3. Based on Cohen's interpretation (Cohen 1988), an effect size of 0.3 represents a small to medium effect and a 21% non-overlap between the two treatment arms.

Patients with missing central Ki67 score at baseline and/or at Week 2 will be excluded from the analysis of the primary efficacy endpoint. For both experimental and control arms, a 6% missing Ki67 rate is assumed. Thus, a total of approximately 215 patients is projected to be enrolled to account for patients with missing Ki67 scores.

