6.4.2 Secondary Efficacy Endpoints

ORR will be defined as the proportion of patients with a CR or PR, as determined by the investigator according to mRECIST (see [Appendix 4](#)). The analysis population for ORR will be all randomized patients with measurable disease at baseline. Patients not meeting the criteria for ORR, including patients without any post-baseline tumor assessment, will be considered as non-responders.

An estimate of ORR and its 95% CI will be calculated using the Clopper-Pearson method for each treatment arm. ORR will be compared between treatment arms using the stratified Cochran-Mantel-Haenszel test. The stratification factors to be used will be the same as those used for randomization. The difference in ORR between treatment arms will be calculated, and its 95% CI will be calculated using the normal approximation to the binomial distribution.

CCCA rate is defined as the proportion of patients with centrally measured Ki67 score $\leq 2.7\%$. CCCA rate at Week 2 will be summarized. The difference in CCCA rates between treatment arms will be calculated, and its 95% CI will be calculated using the normal approximation to the binomial distribution. Patients with missing central baseline and/or Week 2 corresponding Ki67 score will be excluded from the analysis.

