6.4.3 Exploratory Efficacy Endpoints

CCCA rate is defined as the proportion of patients with centrally measured Ki67 scores $\leq 2.7\%$. CCCA rate at surgery will be summarized. The difference in CCCA rates between treatment arms will be calculated, and its 95% CI will be calculated using the normal approximation to the binomial distribution. Patients with missing central baseline and/or Week 2 corresponding Ki67 scores will be excluded from the analysis.

pCR rate is defined as the proportion of patients who achieved pCR in breast and axilla (with pCR defined as the absence of any residual invasive cancer on hematoxylin and eosin evaluation of the resected breast specimen, and all sampled ipsilateral lymph nodes following completion of neoadjuvant systemic therapy [i.e., ypT0/is, ypN0 in the current American Joint Committee on Cancer staging system]) after completion of neo-adjuvant treatment.

The pCR rate will be analyzed using statistical methods similar to those used for ORR.

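### The normal-approximation confidence interval carried over to the pCR difference has zero width when neither arm has an event, and can under-cover when rare pCR rates differ

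*Combined protocol and SAP*

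**What the plan says.** pCR is an exploratory efficacy endpoint. Section 2.1.3 lists it as a comparison between arms: "Pathological complete response (pCR) rate (ypT0/is, ypN0) of GDC-9545 plus palbociclib compared with anastrozole plus palbociclib". Section 6.4.3 gives the method in one line: "The pCR rate will be analyzed using statistical methods similar to those used for ORR".

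Section 6.4.2 sets out the ORR methods, which have three parts:

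- **Per arm:** "An estimate of ORR and its 95% CI will be calculated using the Clopper-Pearson method for each treatment arm".
- **Test:** "ORR will be compared between treatment arms using the stratified Cochran-Mantel-Haenszel test".
- **Difference:** "The difference in ORR between treatment arms will be calculated, and its 95% CI will be calculated using the normal approximation to the binomial distribution".

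For pCR, neither section names another interval, a rule for zero events or a rule for sparse data. No expected pCR rate is stated anywhere.

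**The concern.** The ORR method was chosen for an endpoint whose cited rates are 41% and 55.3% (Section 1.5.3). pCR is stricter: Section 6.4.3 requires no residual invasive cancer in the resected breast and in all sampled ipsilateral nodes. If pCR is rare, the normal approximation for the difference rests on a handful of events or none.

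Two things can then go wrong. With no events in either arm, the estimated variance is zero and the report would show a difference known without error. With a few events and unequal true rates, the interval can miss the true difference more often than 5% of the time. At stake is the stated precision of the pCR comparison. The primary analysis is not involved.

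**Working it through.** **Inputs.** Section 6.1: "Thus, a total of approximately 215 patients is projected to be enrolled to account for patients with missing Ki67 scores". Section 4.2 sets 1:1 allocation. The sample size reproduces: with effect size 0.3, one-sided 10% and 80% power, n per arm = 2 × (1.2816 + 0.8416)² / 0.3² = 100.2, so 101 per arm and 202 in total; 202 / 0.94 = 214.9, so 215. I use n = 107 per arm (215 / 2 = 107.5). The true pCR rates of 0.5% to 5% below are assumptions.

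**Formula.** Section 6.4.2 does not say whether the variance is pooled. I read it as unpooled, without continuity correction: (p1 − p2) ± 1.96 × √[p1(1 − p1)/n1 + p2(1 − p2)/n2].

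**No events in either arm.** With p1 = p2 = 0 the square root is 0, so the interval is [0, 0] at any sample size. A pooled variance is also 0. For comparison, at 0/107 in each arm:

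- Clopper-Pearson upper limit per arm: 1 − 0.025^(1/107) = 3.4%.
- Newcombe interval for the difference: ± 1.96² / (107 + 1.96²) = ± 3.84 / 110.84 = ± 3.5 points.
- Miettinen-Nurminen: k = 3.84 × 214 / (213 × 107) = 0.0361, and k / (1 + k) gives ± 3.5 points.

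The planned table would therefore show two arms each uncertain up to 3.4%, beside a difference of 0 with no uncertainty.

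**How likely that is.** With true rate p in both arms, the chance is (1 − p)^214: 34% at 0.5%, 12% at 1% and 1.3% at 2%.

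**Coverage of the nominal 95% CI for the difference**, by exact enumeration of both binomials at 107 per arm:

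| True pCR rates | Normal approximation | Newcombe |
|---|---|---|
| 0.5% vs 1% | 79% | 99.9% |
| 0.5% vs 2% | 88% | 99% |
| 1% vs 2% | 88% | 99% |
| 1% vs 4% | 92% | 97% |
| 1% vs 3% | 94% | 98% |
| 1% vs 5% | 94% | 98% |

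At 0.5% vs 1%, most of the shortfall is the zero-event case itself: 0.995^107 × 0.99^107 = 0.585 × 0.341 = 20%, and [0, 0] misses the true difference of 0.5 points every time.

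**Equal true rates.** Coverage is 99.7% at 0.5%, 98.4% at 1%, 95.8% at 2% and 94.5% at 5%. The chance of wrongly excluding zero is therefore 0.3%, 1.6%, 4.2% and 5.5%.

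**Check on ORR.** At 41% vs 55.3% (108 and 107 patients), coverage is 94.7%. The method is adequate for ORR.

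**The case against.** Most of the pCR analysis is sound, and several stronger readings fail.

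- **All pCR intervals are unreliable.** A reader might infer this, but the per-arm intervals are Clopper-Pearson and remain valid. Printed beside a 0 to 0 difference, they would alert a careful reader. Only the difference interval is affected.
- **The method produces false positives.** A tempting example is 0 vs 4 events in 107 per arm: the planned interval, −7.3 to −0.1 points, excludes zero, while Newcombe, −9.2 to +0.4, does not. But Miettinen-Nurminen, an equally acceptable score interval, also excludes zero (upper limit about −0.2 points, z = 2.01). The example shows reasonable methods differing at the margin. The equal-rate results above show no material inflation.
- **The stratified test breaks down.** The three two-level factors in Section 4.2 give eight strata, and many may have no pCR. A stratum without events carries no information about the arm difference, and giving it no weight is how Cochran-Mantel-Haenszel works. Nothing here shows an error in that test.

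Three further points reduce the weight. Rarity is assumed. The shortfall is mostly one to three points once one arm reaches 3% to 5%. The endpoint is exploratory, in a study that Section 6.8 describes as hypothesis-generating.

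It can also be said that similar does not mean identical, so a score interval would be compatible with the text. That is true, but none is named. In an open-label trial the choice would then be made with results in view. What stands against the plan is narrow: the only difference interval it specifies fails in a plausible case.

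**Conclusion.** The point holds for the between-arm pCR difference interval alone. The zero-width result with no events in either arm is certain under the plain formula, with pooled or unpooled variance. How often it would arise, and how far coverage falls when rare rates differ, depend on assumed pCR rates, because the documents give none. The problem is substantial when both rates are 2% or lower and differ, and small at most higher rates considered. The coverage figures also assume about 107 patients per arm, unpooled variance and no continuity correction.

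Severity is low. pCR is exploratory, and the primary Ki67 analysis, the sample size and the ORR analysis are unaffected.

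**What to change.** In Section 6.4.3, state that the 95% CI for the between-arm pCR difference will be a score-type interval in place of the normal approximation. Name either Newcombe or Miettinen-Nurminen, and fix the choice before results are seen. State also that the per-arm intervals remain Clopper-Pearson. The ORR text in Section 6.4.2 can stay as it is.

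This costs one sentence and needs no new data or patients. The downside is a slightly wider, conservative interval at very low rates, such as Newcombe coverage of 99% or more at 0.5% vs 1%.

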6.5 SAFETY ANALYSES

All safety analyses will be based on the safety-evaluable population, defined as all patients who receive any amount of study treatment, with patients grouped according to treatment received.

6.5.1 Analyses of Exposure, Adverse Event, Laboratory, and Vital Sign Data

The frequency, nature, and severity of treatment-emergent adverse events, adverse events leading to death, adverse events leading to study drug discontinuation and dose modification, serious adverse events, and adverse events of special interest will be summarized by treatment arm. All deaths will be summarized. Selected laboratory data will be summarized by treatment received and grade compared with baseline, and measurements outside of the normal range will be identified. Relevant vital signs will be presented using summary statistics by treatment received. Drug exposure will also be summarized, including duration of treatment, cumulative dose, and dose intensity.

Treatment-emergent adverse events are defined as adverse events that occur after the first dose of study treatment. Adverse events will be summarized by mapped MedDRA preferred terms and appropriate MedDRA hierarchy. Adverse event severity will be graded according to NCI CTCAE v5.0. Multiple occurrences of the same event will be counted once at the maximum severity.

6.5.2 Exploratory Analyses of Patient-Reported Outcome Data

PRO-CTCAE

PRO-CTCAE analyses will be descriptive, with a focus on characterizing the pattern of symptomatic treatment toxicities during the course of the study. The number and percentage of patients who report each symptom and the change from baseline by category (frequency of occurrence, severity, or interference) will be summarized at each assessment timepoint by treatment arm. For items that are rated on a 5-point Likert scale, the maximum post-baseline score and change from baseline will be summarized by treatment arm.

Results from these exploratory analyses will be presented separately from the safety analyses. PRO-CTCAE data will be analyzed at the item level in line with current NCI recommendations for data handling (Basch et al. 2014). Graphical representation of PRO-CTCAE data over time will also be provided. PRO-CTCAE data will be summarized over time. These analyses will also apply to the “overall treatment burden” item. The proportion of missing data at each assessment timepoint will also be summarized to facilitate interpretation of data.

CTSQ

CTSQ analyses will be descriptive, summarizing means for each domain score (Expectations of Therapy, Feelings about Side Effects, and Satisfaction with Therapy) by treatment arm. The proportions of missing data will also be presented. CTSQ data may also be analyzed in relation to clinical outcomes and PRO-CTCAE scores; item-level responses may be descriptively explored as well.

6.6 PHARMACOKINETIC ANALYSES

Individual and mean plasma concentration of GDC-9545 versus time data will be tabulated and plotted. Additional PK analyses may be conducted as appropriate and reported in a standalone report.

6.7 BIOMARKER ANALYSES

Although no formal statistical analysis of exploratory biomarkers will be performed, data may be analyzed in the context of this study and in aggregate with data from other studies. Results will be presented in a separate report.

6.8 OPTIONAL INTERIM ANALYSIS

Given the hypothesis-generating nature of this study, the Sponsor may choose to conduct an interim efficacy analysis. The decision to conduct an optional interim analysis and the timing of the analysis will be documented in the Sponsor's trial master file prior to the conduct of the interim analysis. The interim analysis will be performed and interpreted by the Sponsor study team personnel who will have full access to unblinded data. Access to treatment assignment information will follow the Sponsor's standard procedures.

7. DATA COLLECTION AND MANAGEMENT

7.1 DATA QUALITY ASSURANCE

The Sponsor will be responsible for data management of this study, including quality checking of the data. Data entered manually will be collected via EDC through use of eCRFs. Sites will be responsible for data entry into the EDC system. In the event of discrepant data, the Sponsor will request data clarification from the sites, which the sites will resolve electronically in the EDC system.

The Sponsor will produce an EDC Study Specification document that describes the quality checking to be performed on the data. Central laboratory data will be sent directly to the Sponsor, using the Sponsor's standard procedures to handle and process the electronic transfer of these data.

eCRFs and correction documentation will be maintained in the EDC system's audit trail. System backups for data stored by the Sponsor and records retention for the study data will be consistent with the Sponsor's standard procedures.

7.2 ELECTRONIC CASE REPORT FORMS

eCRFs are to be completed through use of a Sponsor-designated EDC system. Sites will receive training and have access to a manual for appropriate eCRF completion. eCRFs will be submitted electronically to the Sponsor and should be handled in accordance with instructions from the Sponsor.

All eCRFs should be completed by designated, trained site staff. eCRFs should be reviewed and electronically signed and dated by the investigator or a designee.

At the end of the study, the investigator will receive patient data for his or her site in a readable format that must be kept with the study records. Acknowledgement of receipt of the data is required.

7.3 SOURCE DATA DOCUMENTATION

Study monitors will perform ongoing source data verification and review to confirm that critical protocol data (i.e., source data) entered into the eCRFs by authorized site personnel are accurate, complete, and verifiable from source documents.

Source documents (paper or electronic) are those in which patient data are recorded and documented for the first time. They include, but are not limited to, hospital records, clinical and office charts, laboratory notes, memoranda, patient-reported outcomes, evaluation checklists, pharmacy dispensing records, recorded data from automated instruments, copies of transcriptions that are certified after verification as being accurate and complete, microfiche, photographic negatives, microfilm or magnetic media, X-rays, patient files, and records kept at pharmacies, laboratories, and medico-technical departments involved in a clinical trial.

Before study initiation, the types of source documents that are to be generated will be clearly defined in the Trial Monitoring Plan. This includes any protocol data to be entered directly into the eCRFs (i.e., no prior written or electronic record of the data) and considered source data.

Source documents that are required to verify the validity and completeness of data entered into the eCRFs must not be obliterated or destroyed and must be retained per the policy for retention of records described in Section 7.5.

To facilitate source data verification and review, the investigators and institutions must provide the Sponsor direct access to applicable source documents and reports for trial-related monitoring, Sponsor audits, and IRB/EC review. The study site must also allow inspection by applicable health authorities.

7.4 USE OF COMPUTERIZED SYSTEMS

When clinical observations are entered directly into a study site's computerized medical record system (i.e., in lieu of original hardcopy records), the electronic record can serve as the source document if the system has been validated in accordance with health authority requirements pertaining to computerized systems used in clinical research. An acceptable computerized data collection system allows preservation of the original entry of data. If original data are modified, the system should maintain a viewable audit trail that shows the original data as well as the reason for the change, name of the person making the change, and date of the change.

7.5 RETENTION OF RECORDS

Records and documents pertaining to the conduct of this study and the distribution of IMP, including eCRFs, electronic or paper PRO data (if applicable), Informed Consent Forms, laboratory test results, and medication inventory records, must be retained by the Principal Investigator for 15 years after completion or discontinuation of the study or for the length of time required by relevant national or local health authorities, whichever is longer. After that period of time, the documents may be destroyed, subject to local regulations.

No records may be disposed of without the written approval of the Sponsor. Written notification should be provided to the Sponsor prior to transferring any records to another party or moving them to another location.

Roche will retain study data for 25 years after the final study results have been reported or for the length of time required by relevant national or local health authorities, whichever is longer.

8. ETHICAL CONSIDERATIONS

8.1 COMPLIANCE WITH LAWS AND REGULATIONS

This study will be conducted in full conformance with the ICH E6 guideline for Good Clinical Practice and the principles of the Declaration of Helsinki, or the applicable laws and regulations of the country in which the research is conducted, whichever affords the greater protection to the individual. The study will comply with the requirements of the ICH E2A guideline (Clinical Safety Data Management: Definitions and Standards for Expedited Reporting). Studies conducted in the United States or under a U.S. Investigational New Drug (IND) Application will comply with U.S. FDA regulations and applicable local, state, and federal laws. Studies conducted in the European Union or European Economic Area will comply with the E.U. Clinical Trial Directive (2001/20/EC) and applicable local, regional, and national laws.

8.2 INFORMED CONSENT

The Sponsor's sample Informed Consent Form (and ancillary sample Informed Consent Forms such as an Assent Form or Mobile Nursing Informed Consent Form, if applicable) will be provided to each site. If applicable, it will be provided in a certified translation of the local language. The Sponsor or its designee must review and approve any proposed deviations from the Sponsor's sample Informed Consent Forms or any alternate consent forms proposed by the site (collectively, the "Consent Forms") before IRB/EC submission. The final IRB/EC-approved Consent Forms must be provided to the Sponsor for health authority submission purposes according to local requirements.

If applicable, the Informed Consent Form will contain separate sections for any optional procedures. The investigator or authorized designee will explain to each patient the objectives, methods, and potential risks associated with each optional procedure. Patients will be told that they are free to refuse to participate and may withdraw their consent at any time for any reason. A separate, specific signature will be required to document a patient's agreement to participate in optional procedures. Patients who decline to participate will not provide a separate signature.

The Consent Forms must be signed and dated by the patient or the patient's legally authorized representative before his or her participation in the study. The case history or clinical records for each patient shall document the informed consent process and that written informed consent was obtained prior to participation in the study.

The Consent Forms should be revised whenever there are changes to study procedures or when new information becomes available that may affect the willingness of the patient to participate. The final revised IRB/EC-approved Consent Forms must be provided to the Sponsor for health authority submission purposes.

If the Consent Forms are revised (through an amendment or an addendum) while a patient is participating in the study, the patient or a legally authorized representative must re-consent by signing the most current version of the Consent Forms or the addendum, in accordance with applicable laws and IRB/EC policy. For any updated or revised Consent Forms, the case history or clinical records for each patient shall document the informed consent process and that written informed consent was obtained using the updated/revised Consent Forms for continued participation in the study.

A copy of each signed Consent Form must be provided to the patient or the patient's legally authorized representative. All signed and dated Consent Forms must remain in each patient's study file or in the site file and must be available for verification by study monitors at any time.

For sites in the United States, each Consent Form may also include patient authorization to allow use and disclosure of personal health information in compliance with the U.S. Health Insurance Portability and Accountability Act (HIPAA) of 1996. If the site utilizes a separate Authorization Form for patient authorization for use and disclosure of personal health information under the HIPAA regulations, the review, approval, and other processes outlined above apply except that IRB review and approval may not be required per study site policies.

